
1. Early recognition of patients needing specialist postoperative input
	
Royal College of Anaesthetists: Guidelines for the Provision of Anaesthesia Services 2019²⁵
 
 • Provision of Postoperative Care Recommendation 3.23: Mechanisms for the early recognition of patients requiring specialist postoperative input from geriatrician-led services and/or critical care should be developed. These should include patients at risk of or presenting with delirium, multiple medical complications, functional decline or complex discharge planning.

2. Postoperative intravenous iron therapy is indicated in patients with iron deficiency anaemia
	
International consensus statement on Postoperative Anaemia after Major Surgery 2018²⁶
 
 • Postoperative iron therapy: Should postoperative iron therapy be indicated, i.v. formulations are recommended

3. Extended pharmacological VTE prophylaxis is indicated in patients at high VTE risk after major abdominal or pelvic surgery
	
National Institute of Clinical Excellence: Venous thromboembolism in over 16s: reducing the risk of hospital-acquired deep vein thrombosis or pulmonary embolism (NG89) 2018
 
 • Consider extending pharmacological VTE prophylaxis to 28 days postoperatively for people who have had major cancer surgery in the abdomen.

Methods

1. Summary

A prospective, multicentre, study will be delivered by STARSurg Collaborative & EuroSurg Collaborative across Europe. Mini-teams of up to four collaborators (medical students and at least one doctor) per speciality group per data collection period will prospectively collect data over a continuous 14-day period at each participating centre. This will be on consecutive patients undergoing major abdominal surgery, with follow-up to 30 postoperative days. All mini-teams should be supervised by a consultant in surgery.

2. Study Aims:

- **Primary Aim:** To audit compliance to pre-, intra-, and postoperative audit standards in reducing risk of postoperative cardiovascular complication.

- **Secondary Aims**
 - To characterise rates and risk factors associated with postoperative cardiovascular complications following major abdominal surgery in Europe.
 - To explore the association of pre-operative and postoperative anaemia with postoperative cardiovascular complications and short-term outcomes (length of stay, readmission and 30-day mortality).

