 - Staged with a planned return for reoperation (such as but not limited to damage control laparotomy or burns surgery) OR
 - Change in operative plan such that during the first procedure it is determined that a reoperation is necessary, even if the patient was enrolled preoperatively
- **Return to theatre:** Each individual patient should only be included in the study *once*. Patients returning to theatre due to complications following earlier surgery can be included, as long as their indexed procedure has not already been included in the CASCADE audit.

You should collect data on consecutive patients operated at your centre during the data collection period. This means that all eligible patients should be included.

Strategies to identify consecutive eligible patients could include:

- *Daily review of elective theatre lists.*
- *Daily review of handover sheets/ emergency admission and ward lists.*
- *Daily review of theatre logbooks (both elective and emergency).*

6. Covariates:

Data will be collected on audit standards and confounding factors for risk-adjusted analyses. These include age, sex, ethnicity, body mass index, American Society of Anaesthesiologists (ASA) grade, relevant comorbidities, smoking status, anticoagulant or antiplatelet use, preoperative blood test values, and preoperative anaemia management. Variables including operative urgency, operative procedure, operative contamination, use of tranexamic acid, intraoperative blood transfusions used, haemoglobin level at transfusion, duration of procedure and post-operative iron therapy will also be collected. Without appropriately adjusting for risk factors, it is likely that any findings would be biased and unable to be appropriately analysed on a national scale. A full list of required data fields is available in **Appendix B**, and on the REDCap database.

7. Outcome Measures and Follow-up:

Primary outcome measure:

- Rates of compliance to pre-, intra-, and postoperative audit standards in reducing risk of postoperative cardiovascular complication.

Secondary outcome measures:

- Incidence of postoperative cardiovascular complications within 30-days of surgery according to the Standardized Endpoints for Perioperative Medicine (StEP) cardiovascular.¹³ (see **Appendix D: Definitions of Key Outcomes**).
- 30-day postoperative blood transfusion rates
- 30-day complication rates defined according to the Clavien-Dindo classification (see **Appendix D: Definitions of Key Outcomes**)

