30-day postoperative COVID status	 None  Yes, preop  Yes, postop <hr style="border-top: 1px dashed black;"/> If preop: Symptomatic?  Yes  No If preop: Vaccinated?  Partial  Full  No	If readmission, what was Hb	 ___g/L  Not available	If readmission, anaemia intervention	 None  Iron supplement (Oral / IV ?)  RBC transfusion (if RBC:  1  2  3  4  ≥5 units)
Postoperative outpatient VTE prophylaxis duration	___ days	Postoperative outpatient VTE prophylaxis			 None  LMWH  Warfarin  DOACs (if DOAC:  dabigatran  rivaroxaban  apixaban  edoxaban  betrixaban)

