2. Critical care bed days (if yes)	Number (days from first post-operative day to day of discharge from critical care. If the patient has not been discharged prior to the end of 30-day follow-up, enter '31').	
3. Postoperative haemoglobin	Not applicable / Available (day 0-1, day 1-3, day 4-6, last prior to discharge) If available, please state value in grams/litre	
4. Postoperative interventions for anaemia	None / iron supplementation / Tranexamic acid / RBC transfusion (If yes: 1, 2, 3, 4, ≥5 units)	
5. Cardiovascular complications within 30 days	None / Myocardial infarction / Myocardial injury / Non-fatal cardiac arrest / Coronary revascularisation / Pulmonary embolism (symptomatic non-fatal / asymptomatic) / Deep venous thrombosis (proximal / distal; if either symptomatic / asymptomatic) / New onset Atrial fibrillation / Stroke (select all that apply) *see Appendix D for definitions Please indicate the POD of the event(s) selected.	• Clinical notes • PACS software
6. Bleeding complications within 30 days	None / Major bleeding / Clinically relevant non-major bleeding *see Appendix D for definitions	
7. Post-operative length of stay	Number (days between from the first post-operative day to day of discharge. If the patient has not been discharged prior to the end of 30-day follow-up, enter '31').	
8. Highest 30-day complication grade	None / Clavien-Dindo Grade I-V (see Appendix D for the full 7-point Clavien-Dindo scale). If grade V, was death cardiac, PE or non-cardiac? (see Appendix D for definitions)	
9. 30-day Reoperation	Yes / No	
10. 30-day Readmission	Yes - planned / Yes- unplanned / No (this applies if patient had died during initial admission) If yes: what is the grade of complication (none, grade I, grade II, grade III, grade IV, grade V)	
11. 30-day postoperative COVID status	None / Preoperative / Postoperative If preoperative: are you still symptomatic (yes/no) and were you vaccinated (no / partial / full)	
12. Haemoglobin on readmission	Not available / Available If available, please state value in grams/litre	
13. Interventions for anaemia at readmission	None / iron supplementation (Oral / Intravenous), blood transfusion (If yes: 1, 2, 3, 4, ≥5 units)	
14. Postoperative outpatient VTE prophylaxis duration	Number (days of pharmacological VTE prophylaxis the patient was discharged home with)	

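### As printed, the index-stay field records postoperative iron without its route, although post-operative standard 2 audits intravenous iron

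*Protocol*

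**What the plan says.** **The standard.** In the protocol's Audit Standards table, post-operative standard 2 is "Postoperative intravenous iron therapy is indicated in patients with iron deficiency anaemia". The consensus recommendation cited beside it also concerns route: where postoperative iron is indicated, it favours intravenous formulations.

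**Its role.** Methods 7 gives the primary outcome as "Rates of compliance to pre-, intra-, and postoperative audit standards in reducing risk of postoperative cardiovascular complication". Standard 2 is one of the postoperative standards it covers.

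**What is collected for the index stay.** Appendix B, post-operative field 4, is titled "Postoperative interventions for anaemia" and offers "None / iron supplementation / Tranexamic acid / RBC transfusion". Transfusion is broken down by number of units; iron is not broken down at all. Appendix A, Section 3, has the same undivided iron tick in the box labelled IDA mx. Methods 6 says only that "duration of procedure and post-operative iron therapy will also be collected".

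**What is collected at readmission.** Here route is asked: "iron supplementation (Oral / Intravenous), blood transfusion" in Appendix B, post-operative field 13, and "Iron supplement (Oral / IV" in the matching box of Appendix A.

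**Where the complete field list is.** Methods 6 states: "A full list of required data fields is available in Appendix B, and on the REDCap database". The REDCap screens are not part of the document.

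**The concern.** The standard's distinguishing feature is route, and route is what the index-stay field leaves out. Pre-operative standard 5 already cites a recommendation for iron both before and after surgery with no route named. Without route, standard 2 adds little beyond the postoperative half of that recommendation.

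This cannot be left to an analysis plan. Such a plan can define numerators and denominators, but it cannot create a variable that was not recorded. The completeness rule in Methods 11 does not help, since a fully completed record still lacks route. Filling it in afterwards would be awkward: Methods 8 has paper copies destroyed after upload, and Methods 10 keeps identifiers off REDCap unless explicitly permitted.

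At stake is one component of the primary outcome. If the tick were read as compliance, a unit that gives only oral iron could be credited with meeting an intravenous standard, both in the pooled result and in the local presentation that each centre must give.

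**Working it through.** The plan states no figure for this point, so there is none to reproduce. The check compares the standard with every printed field that touches it, then asks what the tick can and cannot show.

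**Step 1. Fields against the standard.**

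| Element of standard 2 | Printed field | Enough? |
|---|---|---|
| Postoperative iron, index stay | Appendix A, IDA mx; Appendix B, post-operative field 4 | Yes, for iron by any route |
| Given intravenously, index stay | None | No |
| Given intravenously, at readmission | Appendix A readmission box; Appendix B, post-operative field 13 | Yes, but only for readmitted patients and iron given then |
| Patient has iron-deficiency anaemia | Haemoglobin only | No |

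The two forms agree with each other: both omit route for the index stay and both print it for readmission. An extraction fault is therefore an unlikely explanation.

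**Step 2. Counts from the text.**

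- Standards: 5 pre-operative + 1 intra-operative + 3 post-operative = 9, of which 1 is affected.
- Postoperative iron fields in Appendix B: 2 (fields 4 and 13), of which 1 records route.
- Blood tests: pre-operative field 19 lists 3 (haemoglobin, albumin, creatinine). Field 20 lists 7, including those 3. That makes 7 distinct tests, of which 0 are iron studies.
- Pre-operative field 16 records how iron-deficiency anaemia was managed, not whether it was present. Its None option covers both patients without the condition and patients with it who went untreated.

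**Step 3. Numerator, with the denominator held fixed.** Let n_iv be the patients given intravenous iron, n_oral those given oral iron only, and N any common denominator.

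- Tick count = n_iv + n_oral
- Tick rate − intravenous rate = (n_iv + n_oral)/N − n_iv/N = n_oral/N ≥ 0, and zero only if n_oral = 0

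Equivalently, if a share *a* of N has the tick and an unknown fraction *s* of those had it intravenously, the intravenous rate is a × s with s anywhere from 0 to 1. For assumed any-iron rates (not in the protocol):

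| Assumed any-iron rate | Possible intravenous rate |
|---|---|
| 5% | 0% to 5% |
| 10% | 0% to 10% |
| 20% | 0% to 20% |
| 40% | 0% to 40% |

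The width of each range does not depend on sample size, so the roughly 6000 patients expected under Methods 9 would not narrow it.

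**Step 4. Denominator.** The listed fields do not identify patients with iron-deficiency anaemia, so a haemoglobin-based proxy would have to stand in. It also takes in anaemia of other causes. Let D be the true denominator and D′ the proxy, and suppose no iron is given outside D. The tick rate on D′ exceeds true compliance only when (n_iv + n_oral)/n_iv > D′/D. With invented numbers D = 100, n_iv = 40 and n_oral = 10:

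- True compliance = 40/100 = 40%, and (40 + 10)/40 = 1.25
- D′ = 200 (ratio 2.0): tick rate = 50/200 = 25%, below 40%
- D′ = 110 (ratio 1.1): tick rate = 50/110 = 45.5%, above 40%

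The net direction against true compliance therefore depends on quantities that the documents do not give.

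**The case against.** **The database may hold what the print omits.** Methods 6 places the field list in REDCap as well as in Appendix B, and the printed appendices are visibly incomplete: Methods 6 lists ethnicity among the data collected, yet neither appendix has a field for it. A reader might infer that the intravenous numerator cannot be counted at all. The document does not support that, because a route item could exist on the database. The objection stands to this extent: the point is confined to the printed fields. A data dictionary that omits route is still a gap.

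**Overstated compliance does not follow.** A reader might infer that the reported rate must be too high. That holds only on a common denominator (Step 3). With a proxy that includes anaemia without iron deficiency, the rate can fall on either side of true compliance (Step 4). This objection stands in full.

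**Nothing says the tick will be scored as compliance with standard 2.** Correct. It could be reported as iron by any route, which is auditable. The harm is conditional on how the rate is labelled. What is not conditional is that the printed fields cannot yield the intravenous rate.

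**Adding route leaves the denominator unresolved.** Also correct. It repairs the numerator only, so the remedy needs a stated denominator as well.

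**Conclusion.** The mismatch is real on the printed text. Standard 2 is specific to intravenous iron and belongs to the primary outcome, but the index-stay field in both appendices records iron without route, and the readmission field cannot fill the gap. From the printed fields, the intravenous rate for the index stay is bounded only between zero and the any-iron rate.

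The size of the discrepancy cannot be derived from the document. On a fixed denominator, scoring the tick as compliance would give a rate too high by the share given oral iron only, and exact if that share is zero. Against true compliance among patients with iron-deficiency anaemia, the direction is unknown.

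The conclusion assumes that REDCap mirrors the printed fields on this item. If it already records route, what remains is a documentation gap plus the denominator question. Only one of nine standards is affected, so this is a local defect that is worth correcting, not a threat to the primary outcome as a whole.

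**What to change.** 1. Check REDCap. Unless it already records route, add the oral / intravenous option from post-operative field 13 to post-operative field 4, in REDCap, Appendix A and Appendix B. If REDCap already has it, bring the two appendices into line.
2. Count only intravenous iron towards standard 2.
3. If the field cannot be changed, report the result as postoperative iron by any route and do not present it as compliance with an intravenous standard.
4. In either case, label the denominator as a haemoglobin-based proxy: anaemia below a fixed cut-off, on a named haemoglobin reading. State that it includes anaemia without iron deficiency.

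**Cost.** One option on one existing field, a route look-up for patients given postoperative iron, and a sentence on the denominator. The fallback in item 3 needs no new data but gives up the intravenous rate. Neither route identifies iron deficiency itself; that would need iron studies or a diagnosis flag, which the listed fields do not contain.

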 - To characterise the efficacy and safety profile of extended pharmacological thromboprophylaxis in patients at high risk for VTE.

3. Project Timeline:

- The suggested overall data collection periods will be Monday 24th January 2022 to 3rd April 2022. Each mini-team will collect data over a 14-day, consecutive period with subsequent 30-day follow-up:
 - Period 1: 00:00 24th Jan 2022 - 23:59 06th Feb 2022 (+ 30 Day Follow-up)
 - Period 2: 00:00 07th Feb 2022 - 23:59 20th Feb 2022 (+ 30 Day Follow-up)
 - Period 3: 00:00 21st Feb 2022 - 23:59 06th Mar 2022 (+ 30 Day Follow-up).
 - Period 4: 00:00 07th Mar 2022 - 23:59 20th Mar 2022 (+ 30 Day Follow-up).
 - Period 5: 00:00 21st Mar 2022 - 23:59 03rd Apr 2022 (+ 30 Day Follow-up).
- Patients should be included if their operation started (defined as 'knife-to-skin' time) within

the time period during the data collection periods as specified above.

- Additional data collection periods may be added later in the study, to give flexibility to include further centres, who have had logistical difficulties in study start up.
 - Period 6: 00:00 18th Apr 2022 - 23:59 01st May 2022 (+ 30 Day Follow-up).
 - Period 7: 00:00 2nd May 2020 – 23:59 15th May 2022 (+ 30 Day Follow-up).

4. Centre Eligibility:

- CASCADe is open to any hospital in UK and Europe that routinely performs either elective and emergency major abdominal surgery.
- All participating centres are required to register the CASCADe audit according to local regulations. In the UK, CASCADe has been confirmed by the NHS East of Scotland REC Committee that it does not need NHS ethical review under the terms of the Governance Arrangements for Research Ethics Committees (**Appendix F**).
- Internationally, individual study investigators are responsible for ensuring the correct audit, ethical or departmental approval has been achieved prior to commencing data collection (this can be registered as an audit, quality improvement project or service evaluation, if appropriate).
- Evidence of successful audit registration must be sent to study management team (or the appropriate regional lead for UK centres) prior to commencement of data collection. Centres will not be allowed to upload patients’ data onto REDCap without evidence of successful registration of the study.
- Following completion of the CASCADe audit, it is a requirement of participation that mini-teams should **present the audit findings** to the surgery and/or audit departments at each centre.

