Based on previous STARSurg and EuroSurg studies, CASCADE is anticipated to include around 300 centres in Europe. With consideration to recent figures provided by previous STARSurg and EuroSurg studies, it has been estimated that, on average, ten patients will undergo surgery per week at each participating centre. Therefore, a sample of approximately 6000 patients is anticipated. No surgeon-, hospital- or country-specific comparisons will be performed. Further secondary analyses may be performed at the Study Management Group discretion.

10. Local Project Registration:

At European centres, if the option is available, this project may be registered as clinical audit, quality improvement project or service evaluation. Alternatively, it may be necessary to obtain formal ethical approval. It is the responsibility of the local mini-team at each site ensure that the study is registered appropriately, according to local regulations. CASCADE should be registered in the UK and ROI as a clinical audit. It is the responsibility of the local mini-team at each site to identify a local consultants in surgery, anaesthesia or critical care to supervise them and ensure registration.

Confirmation that ethical review is not required for CASCADE within the UK is available in **Appendix F**. Examples of audit registration forms can be found at the online project hub. When registering CASCADE as a clinical audit you can emphasis that:

- CASCADE is a national audit, and all data collected will measure current practice.
- No changes to normal patient pathways/ treatment will be made.
- All CASCADE data will be collected and stored online through a secure server running the

Research Electronic Data Capture (REDCap) web application.²⁸ REDCap allows collaborators to enter and store data in a secure system. Collaborators will be given secure REDCap project server login details, allowing secure data storage on the REDCap database.

Collaborators in the UK should seek their trust's Caldicott Guardian's permission to submit data to the REDCap system. **No data should be uploaded to REDCap prior to written approval from the Caldicott Guardian.** No patient identifiable information (e.g. NHS numbers) should be uploaded or stored on the REDCap database without explicit permission from the trust's Caldicott Guardian. All data should be handled in accordance with national and local data governance policies.

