Appendix B: Data Dictionary

Pre-operative Data Fields	Required data (definition / comment)	Suggested source(s)
1. Patient age	Years (whole years at the time of operation)	– Clinical letters / notes
2. Patient sex	Male / Female	– Clinical letters / notes
3. Patient body mass index (BMI)	kg/m² (record to two decimal places)	– Drug charts – Clinical letters / notes
4. Patient ASA grade	Grade I-V (Full ASA classification available at: https://www.asahq.org/resources/clinical-information/asa-physical-status-classification-system)	– Anaesthetic notes
5. Smoking status	Current (≤6 weeks, >6 weeks), Previous, Never	– Admissions clerking – Clinical notes
6. Clinical Frailty scale	1-3 / 4-6 / 7-9 (Full Clinical frailty scale available at: https://www.dal.ca/sites/gmr/our-tools/clinical-frailty-scale.html)	– Admissions clerking – Clinical notes
7. History of cardiovascular disease	Yes (myocardial infarction, angina, congestive cardiac failure, TIA/stroke, hypertension, peripheral vascular disease, atrial fibrillation, VTE, pulmonary embolism) / No If congestive cardiac failure, what is the NYHA: I / II / III / IV	– Admission clerking – Anaesthetic notes – Outpatient letters
8. History of respiratory disease	None / Dyspnoea on exertion or CXR (mild COPD) / Dyspnoea limiting exertion to <1 flight or CXR moderate COPD / Dyspnoea at rest/rate >30 at rest or CXR (fibrosis or consolidation)	
9. History of COPD	Yes / No	
10. History of chronic kidney disease	Yes (I / II / IIIA / IIIB / IV / V) / No	
11. History of liver cirrhosis	Yes / No	
12. History of diabetes mellitus	Yes - Type I / Yes - Type II (diet controlled, tablet controlled, insulin controlled) / No	
13. Active cancer and/or cancer treatment	Yes / No	
14. Inflammatory bowel disease	Yes / No	
15. Previous history of VTE	Yes / No	
16. Management of iron-deficiency anaemia	None / Preoperative iron supplementation / Tranexamic acid / RBC transfusion (If yes: 1, 2, 3, 4, ≥5 units)	
17. Preoperative treatment	Yes (Aspirin, ACEi/ARB, β-blocker, α ₂ agonist, rate controlling CCB, DHP CCB) / No If yes, was medication stopped preoperatively? (No / Yes, stopped preop only / Yes, stopped preop & postop)	– Clinical letters / notes PACS software
18. Preoperative therapeutic anticoagulation	Yes (Low Molecular Weight Heparin (LMWH), Warfarin, Direct acting oral anticoagulants (DOACs)) / No	– Clinical letters / notes PACS software

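### A secondary aim promises the efficacy and safety of extended thromboprophylaxis, but a non-randomised audit with exposure fixed at discharge can support only an association

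*Protocol*

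**What the plan says.** The aim, in section 2 (Study Aims, Secondary Aims), is "To characterise the efficacy and safety profile of extended pharmacological thromboprophylaxis in patients at high risk for VTE".

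Other parts of the protocol bear on it:

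- **Allocation.** Section 10 (Local Project Registration) says "No changes to normal patient pathways/ treatment will be made". Who receives extended prophylaxis is decided locally.
- **Reason for treatment.** Post-operative Standard 3 is headed "Extended pharmacological VTE prophylaxis is indicated in patients at high VTE risk after major abdominal or pelvic surgery". The guideline text cited under it is discretionary and names a narrower group: "Consider extending pharmacological VTE prophylaxis to 28 days postoperatively for people who have had major cancer surgery in the abdomen".
- **Adjustment.** Section 6 (Covariates) says "Data will be collected on audit standards and confounding factors for risk-adjusted analyses" and warns: "Without appropriately adjusting for risk factors, it is likely that any findings would be biased".
- **Risk markers.** Appendix B collects, among others, "Active cancer and/or cancer treatment" and "Previous history of VTE".
- **Exposure and timing.** Post-operative field 14 in Appendix B records the days of prophylaxis supplied at discharge. Field 5 asks for the postoperative day of each cardiovascular event, including PE and DVT. Field 6, on bleeding, asks for no day.

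The neighbouring aim on anaemia is framed as exploring an association. This one is not.

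**The concern.** Efficacy and safety are statements about what a treatment does. Here treated and untreated patients differ by the reason for treatment, because the standard being audited makes VTE risk that reason. A crude difference in VTE therefore mixes the effect of treatment with the risk that prompted it.

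There is also a timing problem. A patient can be classed as exposed only on reaching discharge, but outcomes are counted from surgery to day 30. Events before discharge cannot be consequences of going home with prophylaxis.

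If the aim stands as worded, a difference or a lack of difference in VTE or bleeding could be published as evidence on efficacy or safety that the design does not provide.

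**Working it through.** **1. The plan's own figure.** Section 9 gives about 300 centres and ten patients per centre per week; each mini-team collects for 14 days. 300 × 10 × 2 = 6000, which matches the stated sample. It corresponds to one two-week period per centre. The protocol states no VTE rate, bleeding rate or proportion treated, so every input in steps 2 to 4 is an assumption.

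**2. Confounding by indication (VTE).** Let a risk marker multiply VTE risk by RRc, with prevalence p1 in treated and p0 in untreated patients. The risk ratio is then multiplied by

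B = [1 + p1(RRc − 1)] / [1 + p0(RRc − 1)].

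Assume RRc 1.5 to 3, p1 0.5 to 0.8 and p0 0.3.

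- Mildest: (1 + 0.5 × 0.5) / (1 + 0.3 × 0.5) = 1.25 / 1.15 = 1.09.
- Strongest: (1 + 0.8 × 2) / (1 + 0.3 × 2) = 2.6 / 1.6 = 1.63.

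A true ratio of 0.60 appears as 0.65 to 0.98, and a true ratio of 1.00 as 1.09 to 1.63. This bias hides benefit.

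**3. Counting from surgery when exposure starts at discharge (VTE).** Assume a 30-day risk R of 2%, a fraction f of VTEs before discharge, a share s treated among patients discharged without VTE, no true effect, and no patient with a pre-discharge VTE classed as discharged on prophylaxis.

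- Pre-discharge risk = Rf. Risk after discharge among those event-free = R(1 − f) / (1 − Rf).
- Treated share of all patients = s(1 − Rf). The remainder form the untreated group and include every pre-discharge event.
- f = 0.2, s = 0.3: treated risk 0.016 / 0.996 = 0.01606. Untreated risk (0.004 + 0.7 × 0.016) / (1 − 0.2988) = 0.0152 / 0.7012 = 0.02168. Ratio 0.74.
- f = 0.6, s = 0.7: treated risk 0.008 / 0.988 = 0.00810. Untreated risk (0.012 + 0.3 × 0.008) / (1 − 0.6916) = 0.0144 / 0.3084 = 0.04669. Ratio 0.17.

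This bias mimics benefit. The two run in opposite directions, so even the sign of a crude 30-day difference cannot be interpreted.

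**4. Precision (VTE).** Assume 30% to 40% of 6000 are high risk, half of them treated (900 to 1200 per group), post-discharge VTE of 0.3% to 1.0% untreated, and a true ratio of 0.5. With e0 and e1 the events in untreated and treated patients, SE(log RR) = √(1/e0 − 1/n + 1/e1 − 1/n).

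- Fewest: e0 = 2.7, e1 = 1.35, about 4 events; SE 1.053; 95% CI 0.06 to 3.9.
- Most: e0 = 12, e1 = 6, 18 events; SE 0.498; 95% CI 0.19 to 1.3.

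**5. What the data fields allow.** For VTE, the recorded event day can be set against length of stay (post-operative field 7), so an analysis starting at discharge is possible. For bleeding it is not: without a day, a bleed in hospital and a bleed at home look the same. An analysis plan cannot recover timing that the data form does not request.

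**The case against.** The strongest reply is that this is mostly wording. The verb characterise also opens the descriptive first secondary aim. No hypothesis or power claim is attached, and the listed outcomes are incidences, rates and durations. That is fair, and it is why the remedy is small. But Appendix D introduces bleeding as a safety outcome for studies of anticoagulant treatment, so a treatment-effect reading comes naturally.

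The second reply is that the protocol already deals with confounding. Section 6 foresees adjustment. Appendix B collects much of what makes up VTE and bleeding risk: age, BMI, cancer, prior VTE, inflammatory bowel disease, procedure, urgency, anticoagulants, kidney disease, cirrhosis, haemoglobin and blood loss. This stands. The reason for giving or withholding prophylaxis is not collected, however, so residual confounding cannot be excluded.

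Three stronger readings are tempting, and the documents do not support them.

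- *No analysis plan could help.* A reader might infer this from the small event counts in step 4. Those counts are assumed and could be low, since centres may run more than one period. Few events limit outcome regression, but a propensity model is fitted to treatment, which is not rare under the same assumptions. The adjustment method may properly be set out in the analysis plan.
- *A null or reversed VTE result is to be expected.* A true ratio of 0.5 appears as 1.0 or 1.5 only if treated patients carry two or three times the baseline risk of untreated ones. The aim is already confined to high-risk patients, which narrows that gradient, and the timing bias pulls the other way.
- *Prophylaxis is withheld where bleeding is feared.* This is plausible, but the protocol does not say it.

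The calculations cover VTE only. For bleeding, the case rests on non-random treatment and the missing event day.

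**Conclusion.** The aim as worded claims more than the design can give. Non-random treatment guided by VTE risk, and exposure known only at discharge, are on the face of the protocol. Planned adjustment reduces the confounding but does not convert the contrast into efficacy, and the direction of the net bias is unknown.

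The size is illustrative: a factor of 1.09 to 1.63 against treatment from confounding, and an apparent ratio of 0.17 to 0.74 in its favour from pre-discharge events, both under assumed inputs. The second range is an extreme case, because it places every pre-discharge VTE in the untreated group.

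The point concerns one secondary aim and one data field. It should be corrected because the wording governs what may later be concluded. It does not touch the primary compliance audit.

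**What to change.** Replace the aim in section 2 with wording such as: *In patients at high VTE risk, to describe how often and for how long extended pharmacological prophylaxis is used, and to explore its risk-adjusted association with VTE and with bleeding from discharge to day 30, with 95% confidence intervals.* Add that this association will not be interpreted as efficacy or safety.

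Count events from discharge. For VTE, use the postoperative day already requested in Appendix B. Add the same day field to the bleeding item; without it, bleeding can be reported only as an overall 30-day incidence, not compared by discharge prophylaxis.

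The cost is a more modest claim, two sentences in section 2 and one extra data item. No patient's care changes.
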